6.4.1.2 Assessment of adverse events

All AEs must be elicited, documented and reported by the investigator to the sponsor from the time that a study subject signs the IC form until the end-of-study visit, i.e. 4-21 days after the last dose of study treatment.

SAEs and other significant AEs should be followed up until resolved or until the event is considered a chronic or stable outcome, or both.

AE may be notified to the investigator by the study subject or observed by the investigator clinically, or be an adverse change in laboratory assessment results. The investigator will

evaluate the subject's AEs at each visit by asking a standard question such as "Since you were last asked, have you felt unwell or different from the usual in any way?"

The investigator will assess and record the causality and severity of the AEs. Causality should be assessed in relation to the investigational medicinal product (see criteria for causality and severity below).

Causality criteria:

Related: The temporal relationship of the AE/SAE onset to the administration of the investigational medicinal product makes a causal relationship possible, and other drugs, therapeutic interventions or underlying conditions do not provide a sufficient explanation for the AE/SAE.

Not related: The temporal relationship of the AE/SAE onset to the administration of the investigational medicinal product makes a causal relationship unlikely, or other drugs, therapeutic interventions or underlying conditions provide a sufficient explanation for the AE/SAE.

Severity criteria:

Mild: Discomfort noticed, but it does not affect normal activity.

Moderate: Discomfort sufficient to reduce or affect normal daily activity.

Severe: Incapacitating with inability to work or perform normal daily activity.

From the time that a study subject candidate signs the IC form, newly appearing diagnosed diseases will be recorded on the AE eCRF.

Investigators must report all AEs to the sponsor on a specific AE eCRF irrespective of their assessment of the causal relationship of the investigational medicinal product to the event.

SAEs are by definition AEs and should be elicited in the same way, and also reported on the AE eCRF.

6.4.1.3 Reporting of serious adverse events by the investigator

The investigator must report all SAEs within 24 h of becoming aware of an SAE. SAEs must be reported within 24 h regardless of the time that may have elapsed since the time the event occurred and regardless of the causal relationship of investigational medicinal product to the event.

All SAEs should be reported on an electronic SAE form, which should be completed by the investigator or other relevant study centre personnel and signed by the investigator. Optionally, if the investigator is not able to complete the SAE form electronically, the paper version of the SAE form can be completed and sent by e-mail or faxed to Orion Drug Safety. The SAE reporting contact information can be found on the SAE form and will be filed in the investigator's study file.

If the initial report is reported by phone or e-mail to the study monitor or other contract research organisation (CRO) personnel and the study centre personnel are unable to fill in the SAE form within 24 h, a paper SAE form will be initiated by the person receiving the report.

The investigator must report the SAE on the SAE eCRF as soon as possible. In addition, SAEs should be reported on the AE eCRF.

The minimum criteria for SAE reporting are: the event or outcome meets the SAE definition, the event happens to an identifiable study subject, and the event is reported by an identifiable and qualified reporter (usually an investigator or other qualified study centre personnel)

A follow-up report to an SAE should be prepared if any relevant change in the condition of the study subject occurs after the initial report. The follow-up report should be documented as an update to the initial report.

SAEs that occur after the end-of-study visit (4-21 days after the last dose of study treatment), should be reported on the SAE form, if the investigator feels that there is a reasonable possibility for the event to have been caused by the study subject's participation in the study.

6.4.1.4 Reporting of serious adverse events to competent authorities and ethics committees

The sponsor is responsible for expediting all suspected unexpected serious adverse reactions (SUSARs) as well as other safety issues requiring expedited reporting to the relevant authorities within applicable timelines.

Notification of the ECs about all relevant events (SUSARs, other relevant safety information) will be performed by the CRO as a delegate of the sponsor.

The expectedness evaluation is required for regulatory reporting and it is performed by the sponsor. The expectedness in this study is evaluated against the Reference safety information section in the current ODM-104 Investigator's brochure (days 1-7, groups 1-4) and the Sinemet UK Summary of Product Characteristics (SmPC) (day 7, group 4).

6.4.2 Special situations

The special situations with study treatment are defined as:

- medication error
- overdose
- abuse
- misuse
- interaction

These special situations with study treatment are reported on the Special situations with study treatment eCRF even if there is no accompanying AE. All clinical manifestations in relation to these special situations will be reported as AEs or SAEs at the same time using the corresponding section of the eCRF.

6.4.3 Pregnancy during the study

Whenever it becomes known that a female partner of a subject becomes pregnant during the exposure to study treatments, the outcome of the pregnancy, delivery, postpartum recovery and

the clinical condition of the offspring during the neonatal period should be reported, subject to the partner's consent. A pregnancy follow-up form will be provided to the investigator for completion after the sponsor has received the initial report.

Any case of pregnancy during a clinical study should be reported by the investigator in the same way as an SAE.

6.4.4 Clinical safety assessments

HR, PB and 12-lead ECG will be recorded in the supine position after at least 5 min rest. The time points at which HR, BP and 12-lead ECG are recorded ECG are presented in [Table 3](#).

12-lead ECG will be recorded 3 times within 5 min (1-2 min interval between the measurements) on day 1 pre-dose. The mean of 3 separate 12-lead ECG recordings will be considered as a baseline.

All 12-lead ECG data collected will be stored. Decision on whether or not to analyse all data will be made during or after the study. If additional ECG analysis will be performed, the results may be reported in a separate report.

A physical examination will be performed by the investigator at screening and end-of-study.

6.4.5 Laboratory safety assessments

The following laboratory tests will be taken at the screening visit after at least 10 h of fasting:

Haematology:

- Haemoglobin
- Haematocrit
- Erythrocytes
- Thrombocytes
- Mean corpuscular volume
- Mean corpuscular haemoglobin
- Mean corpuscular haemoglobin concentration
- Leucocytes
- Differential count (lymphocytes, monocytes, eosinophils, neutrophils, basophils)

Clinical chemistry:

- Albumin
- Creatinine
- Alkaline phosphatase
- Alanine aminotransferase

- Aspartate aminotransferase
- Creatine kinase
- Gamma-glutamyl transferase
- Glucose
- Magnesium
- Sodium
- Potassium
- Calcium (albumin corrected)
- C-reactive protein
- Thyroid stimulating hormone
- Total bilirubin

Urinalysis:

- Stick-test: pH, leucocytes¹, nitrites¹, protein, blood¹, glucose (¹ in case of findings, a microscopy examination of urine sediment will be performed)

Serology:

- Human immunodeficiency virus antigen/antibody
- Hepatitis C virus antibodies
- Hepatitis B-surface antigen

Selected laboratory tests

The following selected laboratory tests will be performed on days 1 and 7 in each treatment period, before the first dose:

Haematology:

- Haemoglobin
- Haematocrit
- Erythrocytes
- Thrombocytes
- Mean corpuscular volume
- Mean corpuscular haemoglobin
- Mean corpuscular haemoglobin concentration
- Leucocytes

- Differential count (lymphocytes, monocytes, eosinophils, neutrophils, basophils)

Clinical chemistry:

- Creatine kinase
- Creatinine
- Alkaline phosphatase
- Aspartate aminotransferase
- Gamma-glutamyl transpeptidase
- Alanine aminotransferase
- Total bilirubin
- Sodium
- Potassium
- Magnesium
- C-reactive protein

Urinalysis

- Stick-test: pH, leucocytes¹, nitrites¹, protein, blood¹, glucose (¹in case of findings, a microscopy examination of urine sediment will be performed)

End-of-study laboratory tests

The same laboratory tests as at the screening visit, except determination of thyroid stimulating hormone and albumin, serology tests, urine test for drug abuse and alcohol breath test will be performed.

Alcohol and drug abuse tests during the study

An alcohol breath test will be performed at the screening visit and on admission in each treatment period.

A urine drug abuse test will be performed at the screening visit and on admission in each treatment period.

The reference ranges of the local laboratories will be recorded on the eCRFs by the sponsor. The investigator's assessment of clinical relevance will be documented on the eCRFs.

In case there are clinically relevant findings, control assessments may be performed according to the judgement of the investigator.

Instructions for the collection, handling, storage and transportation of samples will be provided before the start of the study.

7. DATA COLLECTION AND MANAGEMENT

The investigators and study centre personnel will prepare and maintain accurate source data for each study subject about clinical findings specified in the protocol. Source data include e.g. subject records and laboratory results. The data from source documents will be recorded into an electronic data capture (EDC) system, Medidata Rave (Medidata Inc), using eCRFs at the study centre. Externally produced data, if any, will be uploaded directly into the EDC system or transferred to the sponsor at agreed time intervals. All data on the eCRFs must be verifiable in the source data unless eCRF data are declared as source data.

Investigators and other relevant study centre personnel will be trained to use the eCRFs. After completion of training, they are provided with user names and authorised access to enter and correct data on the eCRFs.

Electronic queries about missing, misleading, incomplete or illogical data will appear in the EDC system. An audit trail within the system will track all changes/corrections made. The investigator has to confirm the content of the eCRF with an electronic signature.

Individual data fields in the EDC system may be locked on an ongoing basis during the study. The fields may be unlocked if further updates are needed. When all data have been entered and all queries resolved, the whole database will be locked. Only authorised and well-documented updates to the study data are possible after the database lock.

Further details regarding data collection and management are presented in the data management plan.

8. STATISTICAL METHODS

8.1 Statistical hypotheses

The primary variable for the evaluation of PK of levodopa is AUC_{0-24} . Primary comparison will be made within levodopa dose level groups, between crossover treatment arms levodopa / 12.5, 25 or 37.5 mg of carbidopa and levodopa / 65 mg of carbidopa / 100 mg of ODM-104. Other crossover comparisons will be performed and considered as secondary. Parallel group comparisons may be performed. The conclusions on possible differences between treatments will be based on both overall evaluation of levodopa concentration-time profiles and formal statistical analyses of PK parameters.

$H_0: AUC_{0-24, \text{levodopa/carbidopa/ODM-104}} = AUC_{0-24, \text{levodopa/carbidopa}}$

$H_0: AUC_{0-24, \text{levodopa/carbidopa/ODM-104}} \neq AUC_{0-24, \text{levodopa/carbidopa}}$

8.2 Estimation of sample size

The sample size estimation is based on earlier ODM-104 phase I study 3112003. Sample size is estimated using the AUC_{0-24} . Based on the results from 12 subjects that completed treatment periods with levodopa 100 mg / carbidopa 25 mg / entacapone 200 mg and MR levodopa 100 mg / carbidopa 65 mg / ODM-104 100 mg. The latter treatment arm with ODM-104 and 65 mg of carbidopa increased exposure by 22% (AUC_{0-24} 14022.2 vs. 17092.6). Within subject variability is estimated to be 0.1386 (\sqrt{MSE} in logarithmic scale). It is assumed that MR

levodopa 100 mg / carbidopa 65 mg / ODM-104 100 mg will increase exposure by 40% compared to MR levodopa 100 mg / carbidopa 25 mg.

When the sample size in each sequence is 3 (with a total sample size of 12), a crossover design will have 80% power to detect a difference in means of 0.336 assuming that the within subject variation is 0.139 using a crossover Analysis of variance (ANOVA) with a 0.1 two-sided significance level. To allow drop outs 14 subjects per group and 56 subjects in total will be randomised into this study with 4-treatment, 4-period William's crossover design. This will provide adequate power for the primary comparison.

Replacement subjects may be enrolled (see section 4.5).

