## 6 Determination of sample size

The sample size estimation is based on earlier ODM-104 phase I study 3112003. Sample size is estimated using the  $AUC_{0-24}$ . Sample size estimation is based on the results from 12 subjects that completed treatment periods with levodopa 100 mg / carbidopa 25 mg / entacapone 200 mg and MR levodopa 100 mg / carbidopa 65 mg / ODM-104 100 mg. The latter treatment arm with ODM-104 and 65 mg of carbidopa increased exposure by 22% ( $AUC_{0-24}$  14022.2 vs. 17092.6). Within subject variability is estimated to be 0.1386 ( $\sqrt{MSE}$  in logarithmic scale). It is assumed that MR levodopa 100 mg / carbidopa 65 mg / ODM-104 100 mg will increase exposure by 40% compared to MR levodopa 100 mg / carbidopa 25 mg.

When the sample size in each sequence is 3 (with a total sample size of 12), a crossover design will have 80% power to detect a difference in means of 0.336 assuming that the within subject variation is 0.139 using a crossover ANOVA with a 0.1 two-sided significance level. To allow drop outs 14 subjects per group and 56 subjects in total will be randomized into this study with 4-treatment, 4-period William's crossover design. This will provide adequate power for the primary comparison. In case there are premature discontinuations the sponsor will decide case-by-case whether replacement subjects will be entered into the study. Replacement subjects will be randomized to go through all 4 treatment periods. Discontinued study subjects are not allowed to re-enter the study.

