## 7 General statistical considerations

### 7.1 Analysis populations

The datasets derived from individual study subjects will be classified into following three classes prior to database lock and before carrying out any statistical analyses:

- Modified intention-to-treat (mITT) population: all randomized subjects who have received at least one dose of study treatment. The difference between ITT and mITT is that subjects in mITT will be included to have the treatment actually administered. In ITT, subjects are included in the treatment they were intended to be administered.

- Per-protocol (PP) population: Subjects who have completed the study according to the protocol without major protocol violations.
- Dosing intervals, where subject experience emesis during the treatment period at Day 7 and following dosing intervals during the period, will be removed from analysis using PP population.
- Periods with PK parameters covering entire Day 7 (e.g.  $AUC_{\infty}$ ) will be excluded from the PP population analysis entirely, in case of emesis.
- If the emesis is experienced at time point 14 hours or thereafter during the last dosing interval, the dosing interval and period will be included into the PP population
- Safety population is the same as the modified ITT population.

The role of each population is described in Table 1.

Table 1. Populations that will be used in tabulations and statistical analyses.

| Primary efficacy variable | Secondary efficacy variables | Demographics
Additional variables | Safety variables  |
|---------------------------|------------------------------|--------------------------------------|-------------------|
| PP                        | PP                           | mITT                                 | Safety population |
| mITT                      | mITT                         |                                      |                   |

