## 7.2 Statistical issues

### 7.2.1 Significance level and confidence intervals

90% confidence intervals and p-values will be produced between different treatments. A two-sided significance level of 10% will be considered the level of statistical significance. Confidence intervals and p-values will be presented up to four decimal places.

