#### **7.2.6 Multiplicity**

For the primary comparisons, there is only one primary comparison in each group, thus multiplicity correction is not needed. For secondary comparisons, where several treatments are included, all pairwise comparisons will be adjusted according to Tukey method.

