#### 8.4.1 Primary PK parameter

The primary PK variable for the evaluation of PK of levodopa is AUC0-24 to describe the total levodopa exposure. The primary PK variable will be summarised using descriptive statistics by treatment and analysed using a mixed linear model with 90% CI applicable for the crossover design. The statistical model will include treatment and period as fixed effects and subject as a random effect. Sensitivity analysis adjusted for subject weight and age will be performed.

The following SAS-code for the primary comparison will be applied:

```
proc mixed data=pkparam2 plots=all alpha=0.10;
  class subject trtpcd visit;
  model log_auc = trtpcd visit / ddfm=KR outp=Resid solution;
  random subject;
  lsmeans trtpcd / diff cl alpha=0.10;
  ods output tests3=testCross lsmeans=lsmeansCross
  diffs=diffscross;
  by group;
run;
```

The following SAS-code for the sensitivity analysis will be applied:

```
proc mixed data=pkparam2 plots=all alpha=0.10;
  class subject trtpcd visit;
  model log_auc = trtpcd visit weightkg age / ddfm=KR outp=Resid
solution;
random subject;
lsmeans trtpcd / diff cl alpha=0.10 adjust=tukey ADJDFE=ROW;
ods output tests3=testCross2 lsmeans=lsmeansCross2
diffs=diffscross2;
by group;
run;
```

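### The sample-size inputs give over 99.9% power for the primary comparison, not the stated 80%; 80% power is reached at a ratio of about 1.16, and N stands

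*Protocol*

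**What the plan says.** Protocol section 8.2 takes its variability from study 3112003. It gives a within-subject value of 0.1386, which it labels as the square root of the mean squared error on the log scale. It assumes a 40% increase in levodopa AUC0-24 for the ODM-104 combination over MR levodopa 100 mg with carbidopa 25 mg. It then states that, with 3 subjects in each of four sequences (12 in total), "a crossover design will have 80% power to detect a difference in means of 0.336 assuming that the within subject variation is 0.139". The test behind this figure is an analysis of variance for the crossover at the two-sided 10% level. Each group is raised to 14 to allow for drop-outs, and the section concludes: "This will provide adequate power for the primary comparison".

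SAP section 6 repeats the calculation without change and adds: "In case there are premature discontinuations the sponsor will decide case-by-case whether replacement subjects will be entered into the study". SAP section 7.2.1 confirms the level: "A two-sided significance level of 10% will be considered the level of statistical significance". The analysis model (Protocol 8.4.3, SAP 8.4.1) has treatment and period as fixed effects and subject as a random effect, fitted separately within each group.

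**The concern.** A within-subject SD of 0.139 is small beside a log difference of 0.336, so 12 subjects in a crossover should give far more than 80% power. The sentence is the only place where the plan says what the primary comparison can detect.

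As written, it implies that losing even one of 12 evaluable subjects takes power for a 40% effect below 80%. Two parts of the plan make that number relevant. Replacement of drop-outs is left to the sponsor's judgement. In addition, under SAP section 7.1, periods for parameters covering the whole of day 7 "will be excluded from the PP population analysis entirely, in case of emesis" (later emesis, from 14 hours, is exempt), and the per-protocol population carries the primary conclusions. The sentence also makes the plan look weak for an effect the size of the 22% increase seen in study 3112003, which used a different comparator.

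**Working it through.** **Inputs (Protocol 8.2, SAP 6)**
- Evaluable subjects per group: n = 12
- Log difference: 0.336. Check: ln 1.40 = 0.3365, so this is the assumed 40% increase.
- Within-subject SD: 0.139 (0.1386 rounded)
- Two-sided level: 0.10
- Earlier-study ratio: 17092.6 / 14022.2 = 1.219, which agrees with the stated 22%

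The effect inputs therefore reproduce. The power does not.

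**Error degrees of freedom.** For a complete four-period crossover with subject, period and treatment effects, df = 3(n − 1) − 3. With n = 12 this is 30.

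**Standard error.** SE = SD × √(2/n) = 0.139 × √(2/12) = 0.0567.

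**Power at 0.336.** The noncentrality is 0.336 / 0.0567 = 5.92 and the critical t is 1.697. Noncentral-t power is 99.998%. With only 10 df (a two-sequence crossover of 12) the critical t is 1.812 and power is 99.994%.

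**Difference with 80% power.** With 30 df it is 0.144, and exp(0.144) = 1.155. With 10 df it is 0.152, a ratio of 1.164. Hence about 1.16.

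**Attempts to recover 80%**

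| Reading | Power at 0.336 |
|---|---|
| 0.139 taken as a variance (SD 0.373), n = 12 | 70% |
| Level 0.05 instead of 0.10, n = 12 | 99.96–99.99% |
| Bonferroni for 24 tests, n = 12 | 96.2–99.6% |
| Two-sequence crossover, 3 per sequence (N = 6) | 95.9% |
| Parallel t-test, 3 per arm (4 df) | 78.2% |

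The variance reading also contradicts the section's own label. Only the last row comes near 80%, and it describes neither a crossover nor 12 subjects. It may be where the figure came from, but the documents do not say. Working backwards with n = 12 and 30 df, 80% power at 0.336 requires an SD of 0.323.

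**Fewer or more evaluable subjects, SD 0.139**

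| n | df | Power at ratio 1.40 | Ratio with 80% power |
|---|---|---|---|
| 8 | 18 | 99.9% | 1.20 |
| 10 | 24 | 99.98% | 1.17 |
| 12 | 30 | 99.998% | 1.16 |
| 14 | 36 | over 99.999% | 1.14 |

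For a 22% increase at n = 12, power is about 95% (10 df) to 96% (30 df).

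**If the true SD is larger.** The values 0.20 and 0.25 are my assumptions. As a guide, if the estimate from study 3112003 had 11 error df (not stated), its one-sided 95% upper limit would be 0.1386 × √(11/4.575) = 0.215.

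| SD | n | Power at ratio 1.40 | Ratio with 80% power |
|---|---|---|---|
| 0.20 | 12 | 99.1% | 1.23 |
| 0.25 | 12 | 94.2% | 1.30 |
| 0.25 | 8 | 82.6% | 1.38 |

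**The case against.** The strongest objection is that nothing follows from the error. It is conservative, the adequacy statement is true, and no test, estimate or interval changes. That is correct, and it limits how serious the point is. It does not make the sentence right.

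A second argument is that 80% was a planning target, not achieved power. In a two-sequence crossover with these inputs, 2 per sequence gives 70.3% and 3 per sequence gives 95.9%, so 3 is the smallest whole number that meets an 80% target. Carrying 3 over to four sequences gives 12. This is a plausible account of how the wording arose, but it is inference, and 80% is still not the power of the design described.

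Third, the plan ties replacement to the sponsor's case-by-case decision, not to power, and sets no minimum number of completers. The SAP table templates also show filled-in counts and program dates in May 2017, against a planned start in February 2017, so many such decisions may already have been taken. This stands: the effect on replacement decisions is a possible misreading, not a demonstrated harm.

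Finally, the larger SDs are not in the documents. They appear here only as a labelled sensitivity range, and the finding rests on 0.139 alone.

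**Conclusion.** The stated 80% is wrong in both documents. From the plan's own inputs, power for a ratio of 1.40 is above 99.9% whichever error df are used, and 80% power falls at a ratio between 1.155 and 1.164. The error understates power. The 14 per group remain sufficient, although the calculation as written does not derive 12.

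The result assumes complete data on 12 subjects and that the SD from study 3112003 applies. That SD and the 40% effect are stated for the 100 mg MR comparison and are carried over to the other groups, including group 4 with its IR comparator. Across SDs up to 0.25 and n down to 8, power for a ratio of 1.40 stays above 80%. The point is worth correcting but does not threaten the trial.

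**What to change.** In Protocol section 8.2 and SAP section 6, replace the power sentence with:

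*With 12 completers per group, a within-subject SD of 0.139 and a two-sided 10% level, power for a ratio of 1.40 exceeds 99.9%; 80% power is reached at a ratio of about 1.16. This assumes that the SD from study 3112003 carries over; at an SD of 0.20 the ratio is about 1.23.*

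Leave the sample size, design and analysis as they are. The cost is one sentence in each of two sections.

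If a detectable ratio for the secondary AUC0-24 contrasts is wanted as well, first settle whether they are adjusted. SAP section 7.2.6 says: "For secondary comparisons, where several treatments are included, all pairwise comparisons will be adjusted according to Tukey method". The AUC0-24 code in SAP section 8.4.1 has "lsmeans trtpcd / diff cl alpha=0.10" with no Tukey option. At n = 12 and SD 0.139 the 80%-power ratio is about 1.20 with Tukey (critical value 2.394 on 30 df, log difference 0.185) and about 1.16 without.
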